11.5.4 Psychiatric Diagnostic Screening Questionnaire (PDSQ)

The PDSQ is a brief self-administered instrument to assess DSM-4 Axis I disorders, including alcohol use disorder (AUD) and drug use disorder (DUD). It is the only brief questionnaire assessing DSM-4 substance use disorder that has been validated for self-administration. The PDSQ was validated in more than 3,000 in both medical and mental health outpatient settings.[59-61]

61] There are 6 items assessing AUD and 6 items for DUD, all using a yes/no response format and a 2-week timeframe. The PDSQ is used for baseline and follow-up assessments of AUD, DUD, and depression. Because the PDSQ does not specify drug class (for example, it does not distinguish between cocaine vs. opioid use disorder) the CIDI, rather than the PDSQ, is used to measure DSM-5 OUD. The drawbacks to the PDSQ—namely, that it assesses DSM-IV rather than DSM-V SUDs, and is not specific to drug class—are counterbalanced in this study by the benefits of having a brief instrument that has been validated for self-administration.

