14.1.2 Secondary Objectives

The trial has two secondary objectives, which capture patient-level and provider-level impacts of the STOP intervention.

The patient-level secondary objective (Aim 2) is to examine the impact of STOP on the important patient participant outcomes of moderate-severe OUD, overdose risk behavior and overdose events, alcohol and other drug use, health-related quality of life, mental health, pain symptoms and functioning, sleep, and acute health care utilization. We hypothesize that participants in the STOP condition, in comparison to participants in the EUC condition, will have:

- H2.1 Fewer days of binge alcohol use.
- H2.2 Fewer days of benzodiazepine use.
- H2.3 Fewer days of stimulant use (cocaine and amphetamine-type stimulants).
- H2.4. Fewer days of marijuana use.
- H2.5 Fewer days of other drug use (not including opioids, benzodiazepines, stimulants, and marijuana).
- H2.6 Lower proportion of individuals having increased days of illicit or nonmedical opioid use.
- H2.7. Lower prescription opioid misuse behaviors, among participants receiving prescribed opioids.
- H2.8 Lower incidence of moderate-severe OUD.
- H2.9 Lower rates of non-opioid drug use disorder and alcohol use disorder.

- H2.10 Lower rates of self-reported overdose risk behavior and nonfatal opioid-related overdose events.
- H2.11 No worsening of pain symptoms and pain-related functioning.
- H2.12 Fewer symptoms of depression (including suicidality) and anxiety.
- H2.13 Better sleep quality
- H2.14 Better health-related quality of life.
- H2.15 Lower rates of acute health care utilization (ED and hospital visits).

The provider-level secondary objective (Aim 3) is to characterize the impact of STOP on primary care provider behaviors, including prescribing practices and monitoring of patient participants with subthreshold OUD. Our hypothesis is that providers assigned to the STOP condition, in comparison to providers in EUC, will have over 12 months of follow-up:

- H3.1 Lower rates of prescribing of high-dose opioids (defined as prescriptions totaling >90 morphine milligram equivalents).
- H3.2 Fewer patients with risky opioid use who are prescribed benzodiazepines.
- H3.3 Higher proportion of patients with risky opioid use receiving at least one prescription for a naloxone kit.
- H3.4 Increased monitoring of patients with risky opioid use, defined as: toxicology testing, diagnosis of OUD, and higher visit frequency.

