2.2.2 Secondary Objectives

The trial has two secondary objectives, which capture patient participant-level and provider-level impacts of the STOP intervention.

The patient-level secondary objective (Aim 2) is to examine the impact of STOP on important patient-level outcomes of substance use that increases opioid-related overdose risk (binge alcohol use, benzodiazepine and stimulant use), other drug use, OUD and other drug and alcohol use disorders, overdose risk behaviors and nonfatal overdose events, pain symptoms and related functioning, mental health symptoms (depression, anxiety, suicidality), sleep, health-related quality of life, and acute health care utilization. We hypothesize that patient participants in the STOP condition, in comparison to participants in the EUC condition, will have:

- H2.1 Fewer days of binge alcohol use.
- H2.2 Fewer days of benzodiazepine use.
- H2.3 Fewer days of stimulant use (cocaine and amphetamine-type stimulants).
- H2.4 Fewer days of marijuana use.
- H2.5 Fewer days of other drug use (not including opioids, benzodiazepines, stimulants, and marijuana).
- H2.6 Lower proportion of individuals having increased days of illicit or nonmedical opioid use.
- H2.7 Reduced prescription opioid misuse behaviors, among patients receiving prescribed opioids.
- H2.8 Lower incidence of moderate-severe OUD.
- H2.9 Lower rates of non-opioid drug use disorder or alcohol use disorder.

- H2.10 Lower rates of self-reported overdose risk behavior and nonfatal opioid-related overdose events.
- H2.11 No worsening of pain symptoms and pain-related functioning.
- H2.12 Fewer symptoms of depression (including suicidality) and anxiety.
- H2.13 Better sleep quality.
- H2.14 Better health-related quality of life.
- H2.15 Lower rates of acute health care utilization (ED and hospital visits).

The provider-level secondary objective (Aim 3) is to characterize the impact of STOP on primary care provider behaviors, including medications prescribed, lab tests, diagnosis of OUD, and frequency of medical visits. Our hypothesis is that providers assigned to the STOP condition, in comparison to providers in EUC, will have, over 12 months of follow-up...

- H3.1 Lower rates of prescribing of high-dose opioids (defined as prescriptions totaling >90 morphine milligram equivalents (MME)) to patients with risky opioid use.
- H3.2 Fewer patients with risky opioid use who are prescribed benzodiazepines.

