3.4 Scoring Conventions

For patient participant assessments that require scoring and that will be summarized in the baseline demographic summary (Section 5.2) and/or used as potential covariates (Section 7.4), the following scoring algorithms will be used:

Assessment (eCRF)	Name of Score	Number of Items	Score Range	Scoring Algorithm
Current Opioid Misuse Measure (HLS (baseline), CMM (other timepoints))	COMM Score	17	0-68	Sum of the seventeen 0-4 rated items
Psychiatric Diagnostic Screening Questionnaire (PDQ)	Alcohol Use Disorder Score	6	0-6	Sum of the yes (1)/no(0) alcohol items
Psychiatric Diagnostic Screening Questionnaire (PDQ)	Drug Use Disorder Score	6	0-6	Sum of the yes (1)/no(0) drug items
Overdose Risk Behavior (ORB)	Overdose Risk Behavior Score	9	0-34	Sum of the eight 0-4 rated items and one 0-2 rated item
Brief Pain Inventory Short Form (BPI)	Pain Severity Score	4	0-10	Average of the four 0-10 rated severity items
Brief Pain Inventory Short Form (BPI)	Pain Functioning or Interference Score	7	0-10	Average of the seven 0-10 rated interference items
PROMIS Anxiety Short Form (PMA)	Anxiety Score	8	0-32	Sum of the eight 0-4 rated items
Patient Health Questionnaire-8 (PHQ)	Depression Score	8	0-24	Sum of the eight 0-3 rated items
PROMIS Sleep Disturbance Short Form (PMS)	Sleep Disturbance Score	4	4-20	Sum of the four 1-5 rated items with last two items reversed scored
Short Form 12 (SFM)	Health related Quality of Life (QoL): Overall Score		0-100	Scored using QualityMetric proprietary software
Short Form 12 (SFM)	Health Related QoL: Mental Health Component Score		0-50	Scored using QualityMetric proprietary software
Short Form 12 (SFM)	Health Related QoL: Physical Health Component Score		0-50	Scored using QualityMetric proprietary software

When participants are missing one or more of the items that comprise the score, prorated scores by averaging the available items will be used to compute the score. The prorated score is calculated using the following equation:

$$T_P = \left(\frac{T_R}{N_R} \right) \times N_T$$

where

T_P = Prorated total score

T_R = Total raw score based on those items with a response

N_R = Number of items with a response

N_T = The total number of items which comprise the score.

A prorated score is computed when less than 20% of the items are missing. Otherwise, the score is set to missing.

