 - ii. COMM score, assessed at screening and at 6 and 12 months.
- h. Urine Drug Screens are used to verify self-reported drug use. Urine drug screens are conducted at baseline and at 6 and 12 months.
- i. For participants receiving prescribed opioids, the COMM provides an additional measure of prescription opioid misuse, collected at baseline and at 6 and 12 months.

2. Substance use disorder: Opioid use disorder is assessed at baseline and at 6 and 12 months using the modified World Mental Health Composite International Diagnostic Interview (CIDI). Drug (other than opioid) and alcohol use disorder measures are collected using the PDSQ at baseline and at 6 and 12 months. The PDSQ is used rather than the CIDI for these measures because it is brief and self-administered, which makes it more feasible for these follow-up assessments.
 - a. H2.8. Moderate-severe opioid use disorder (CIDI opioid items)
 - b. H2.9. Drug use disorder (PDSQ drug items)
 - c. H2.9. Alcohol use disorder (PDSQ alcohol items)
3. Overdose risk behaviors and events
 - a. H2.10. Overdose risk behavior and behavioral intention to reduce risk is measured at baseline and at 6 and 12 months (Overdose Risk Behavior Questionnaire)
 - b. H2.10. Episodes of non-fatal overdose are measured at baseline and at 6 and 12 months (Non-Fatal Overdose Questionnaire)
4. Pain symptoms and pain-related functioning
 - a. H2.11. Pain symptoms (severity, impact on functioning) are measured at baseline and at 3, 6, 9, and 12 months using the BPI short form (items #3-6 for pain symptoms and items #9A-9G for functioning).
5. Mental health
 - a. H2.12. Anxiety symptoms are measured at baseline and 6 and 12 months (PROMIS short form)
 - b. H2.12. Depression symptoms and suicidality are measured at baseline and at 6 and 12 months (PHQ-8 and PSS)
 - c. H2.13. Sleep quality is measured at baseline and at 6 and 12 months (PROMIS Sleep 4a)
6. Health-related quality of life and acute health care utilization
 - a. H2.14. Health-related quality of life is measured at baseline and at 6 and 12 months (SF-12)
 - b. H2.15. ED and hospital utilization is measured using participant self-report of acute care events (ED visits, hospitalizations for medical reasons, hospitalizations for detoxification), collected at baseline and at 6 and 12 months.

Measures of provider-level outcomes

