¹ Risky opioid use included nonmedical use of prescribed opioids (taking a higher dose or taking an opioid more frequently than prescribed; taking pharmaceutical opioids that were not prescribed to the individual taking them) or any use of illicit opioids collected on the Healthy Living Monthly baseline survey.

² Alcohol (AUD) and drug use disorder (DUD) scores were measured using the Psychiatric Diagnostic Screening Questionnaire (PDSQ). There are 6 yes (1) or no (0) items for both AUD and DUD. The score for each disorder is the sum of the 6 items. Scores range from 0-6. A score of 1 or greater indicates substance use disorder (DSM-4: abuse or dependence).

³ Pain severity and functioning (interference) were measured using the Brief Pain Inventory (BPI) Short Form. The form asks 11 questions to measure the intensity of pain, and the rate at which pain interferes with daily activities, using a 0 to 10 scale. Pain severity can be measured using the average of the four severity items or the "worst pain" single item. A worst pain item score of 1-4 indicates mild pain, 5-6 moderate pain, and 7-10 severe pain. Pain functioning (interference) is the average of the seven functioning (interference) items.

⁴ The PROMIS Anxiety Short Form is an 8-item self-assessment of anxiety symptoms in the last seven days. The response values of each item are 0-4 Likert rating format (never, rarely, sometimes, often, and always) and the total score is the sum of all items. The score ranges from 0-32.

⁵ Depression symptoms was assessed using the Patient Health Questionnaire (PHQ-8) Depression screening tool. The tool is an 8-item self-assessment the response values of each item are 0-3 Likert rating format (not at all, several days, more than half the days, nearly every day) , and the total score is the sum of the 8 items. The score ranges from 0-24. A score of 5-9 indicates mild depressive symptoms, 10-14 moderate depressive symptoms, 15-19 moderately severe depressive symptoms, and 20-24 severe depressive symptoms.

⁶ Sleep quality over the past seven days was assessed using the PROMIS Sleep Disturbance Short Form. The response values of first item is 1-5 Likert rating format (very good, good, fair, poor, very poor); and remaining three items item use 1-5 Likert rating format (very much, quite a bit, not at all). The item 3 and 4 will be reverse the direction with higher scores indicating worse sleeping quality. The total score is the sum of all items (range from 4-20).

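### H2.9 is worded as an effect on non-opioid drug use disorder, but the PDSQ drug items do not separate opioids from other drugs, so the drug half of H2.9 cannot support a non-opioid conclusion

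*SAP*

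**What the plan says.** The hypothesis in SAP 2.2.2 is "H2.9 Lower rates of non-opioid drug use disorder or alcohol use disorder". Protocol 14.1.2 has the same construct: "H2.9 Lower rates of non-opioid drug use disorder and alcohol use disorder". Protocol 5.2 agrees.

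The instrument is assigned in SAP 7.7: "Drug (other than opioid) and alcohol use disorder measures are collected using the PDSQ at baseline and at 6 and 12 months". Protocol 7.2.1 and 14.2.2 carry the same sentence.

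Protocol 11.5.4 describes the instrument: "There are 6 items assessing AUD and 6 items for DUD, all using a yes/no response format and a 2-week timeframe". It then explains why OUD is measured by the CIDI: "Because the PDSQ does not specify drug class (for example, it does not distinguish between cocaine vs. opioid use disorder". The section closes by weighing the drawbacks, including that the PDSQ "is not specific to drug class—are counterbalanced in this study by the benefits of having a brief instrument".

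SAP 3.4 defines the drug score as "Sum of the yes (1)/no(0) drug items", range 0 to 6. A footnote to the baseline table in the SAP appendix (Table 18) adds: "A score of 1 or greater indicates substance use disorder (DSM-4: abuse or dependence". SAP 7.8 plans a GEE for the PDSQ drug items at 6 and 12 months, accounting for PCP clustering and adjusting for the baseline level of the same measure. It sets no cut-off for this follow-up analysis.

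**The concern.** The outcome is labelled as excluding opioids, and the protocol's own description of the instrument says that this exclusion cannot be made. In a general drug-using sample this might be mostly noise. Here the contaminating component is present by design: risky opioid use is an entry criterion, up to 3 DSM-5 OUD criteria are allowed, and the intervention is built to change opioid behaviour. The opioid contribution to the score may therefore differ between arms.

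What is at stake is a claim of benefit beyond opioids. If STOP reduces opioid problems and leaves other drug problems unchanged, the PDSQ drug measure can still fall, and as H2.9 is worded that fall would support a non-opioid conclusion. The reverse can also happen: a real reduction in other drug problems is diluted when participants remain positive because of opioids.

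**Working it through.** **Is the mismatch repaired anywhere?** I followed H2.9 from hypothesis to analysis.

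- Hypothesis (SAP 2.2.2; Protocol 5.2, 14.1.2): non-opioid.
- Instrument (SAP 7.7; Protocol 7.2.1, 14.2.2): PDSQ, labelled as other than opioid.
- Instrument property (Protocol 11.5.4): no drug class.
- Scoring (SAP 3.4): plain sum of the six items, with no opioid exclusion.
- Analysis (SAP 7.8): adjusted only for its own baseline. That does not remove a change in opioid problems after baseline.

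I found no instruction to participants to disregard opioids, no drug-class follow-up item, no restriction by CIDI result or reported opioid use, and no caveat in the SAP.

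**How large could the effect be?** The plan gives no rate, power or event count for H2.9, so there is no figure to reproduce. All rates below are assumptions.

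Let n be the probability of a positive caused by non-opioid drugs, equal in both arms (true non-opioid effect zero). Let o be the probability of a positive caused by opioids. Taking the two as independent, the measured rate is 1 − (1 − n)(1 − o), so the spurious difference is (1 − n)(o_EUC − o_STOP).

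For n = 0.15 and o = 0.30 in EUC against 0.20 in STOP:

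- EUC: 1 − 0.85 × 0.70 = 0.405
- STOP: 1 − 0.85 × 0.80 = 0.320
- Difference: 0.085, or 8.5 points

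Over a grid (percentage points):

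| n | o 20% vs 15% | o 30% vs 20% | o 40% vs 25% |
|---|---|---|---|
| 10% | 4.50 | 9.00 | 13.50 |
| 15% | 4.25 | 8.50 | 12.75 |
| 25% | 3.75 | 7.50 | 11.25 |

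**Could it reach nominal significance?** From the documents: 300 patients and 20% dropout give 300 × 0.8 / 2 = 120 per arm. The planned fall from 20 to 14 days per 90 is (20 − 14)/20 = 30%; applying this to opioid-caused positives is an assumption. With n = 0.20 and o = 0.40 against 0.28:

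- EUC: 1 − 0.80 × 0.60 = 0.520
- STOP: 1 − 0.80 × 0.72 = 0.424
- Odds ratio: (0.424/0.576)/(0.520/0.480) = 0.68
- Chance of p < 0.05 in a simple two-sided comparison of proportions: 32%
- With an assumed ICC of 0.05 and 5 × 0.8 = 4 evaluable patients per PCP, the design effect is 1 + 3 × 0.05 = 1.15, and the chance is 28%

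Over n of 10–40% and control o of 20–60%, the spurious difference runs from 3.6 to 16.2 points, the odds ratio from 0.87 to 0.52, and the chance of significance from about 8% to 72% (7.5% to 66% with the ICC). The nominal level is 5%. This is a simple approximation to the planned GEE.

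**The opposite direction.** With o = 0.40 in both arms and n falling from 0.15 to 0.10, the measured rates are 1 − 0.85 × 0.60 = 0.49 and 1 − 0.90 × 0.60 = 0.46. A true 5-point non-opioid reduction appears as 3 points.

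**The case against.** The strongest reply is that the limitation is disclosed. Protocol 11.5.4 names the lack of drug-class specificity and accepts it for brevity and self-administration. Since OUD is assessed by the CIDI, that trade-off must concern the PDSQ's role in H2.9. This stands as a reason for using the instrument. It does not justify calling the result other than opioid.

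Several further points stand in part:

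- The H2.9 endpoint lines and the analysis text in SAP 7.8 speak simply of drug use disorder, without the opioid qualifier. The label sits in the hypothesis and the lead-in sentence, so little text needs changing.
- Days of benzodiazepine, stimulant, marijuana and other drug use (H2.2–H2.5) and substance-specific urine results would make an isolated PDSQ change look suspect. But they measure use, not disorder, and nothing links them to H2.9.
- H2.9 is one of many secondary outcomes, to be read in the light of multiple testing. That limits the weight of the point but does not remove it.

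A reader might go further and infer that H2.9 largely repeats the primary outcome or H2.8. The documents do not support that: the share of positives due to opioids alone is unknown, and a participant with another drug problem may stay positive whatever happens to opioid use. Nor do they establish that one positive answer makes a follow-up case. That threshold appears only in the baseline-table footnote, and the covariate table in SAP 7.4 treats the score as continuous. The class problem exists at any cut-off and for the summed score.

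**Conclusion.** The point holds as a mismatch between claim and measure. The plan states a non-opioid hypothesis and labels the measure accordingly, while the protocol says the instrument cannot make that distinction, and no later step repairs it. An arm difference in the PDSQ drug measure can be driven wholly or partly by opioid problems, and a real non-opioid effect can be diluted.

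How far this would happen is unknown. The range of about 4 to 13.5 points (3.6 to 16.2 in the wider grid) rests entirely on assumed rates, independence and a true non-opioid effect of zero. It shows what is possible and does not predict the result. The conclusion about the label does not depend on these figures.

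The alcohol half of H2.9 and the primary analysis are unaffected.

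**What to change.** Restate the drug half of H2.9 as *any drug use disorder, opioids included (PDSQ drug items)* in SAP 2.2.2 and 7.7, and in the matching text of Protocol 5.2, 7.2.1, 14.1.2 and 14.2.2. Changing the SAP alone would create a new discrepancy with the protocol.

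Add to SAP 7.8 that this outcome will not be interpreted as a non-opioid effect, and that evidence on non-opioid drugs comes from H2.2–H2.5 and the substance-specific urine screens, which measure use and not disorder.

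Do not try to rescue the label by counting a PDSQ positive as non-opioid only when the survey shows no risky opioid days. That conditions on a post-randomisation variable STOP is meant to change. Suppose true non-opioid disorder is 15% in both arms, and 30% of EUC and 45% of STOP have no risky opioid days, independently of disorder (assumed). The derived rates are 0.15 × 0.30 = 4.5% and 0.15 × 0.45 = 6.75%, a spurious increase under STOP. The recall periods also differ: 2 weeks for the PDSQ, 30 days for the survey.

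At most, cross-tabulate PDSQ drug positives by arm with reported opioid and non-opioid use. Keep this descriptive, and label it post hoc if it is added after data are seen.

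The cost is some wording in two documents and a narrower claim for H2.9. No new data are needed.

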7.8 Analyses of Secondary Outcome Measures

The DSC will analyze the following secondary outcomes: H2.1, H2.2, H2.3, H2.4, H2.5 and descriptive analysis for urine drug screens. The LN will analyze the rest of the secondary outcomes.

A secondary aim is to evaluate the impact of the STOP intervention on days of alcohol and drug use that increases risk of opioid related overdose. For this aim, those variables will be analyzed separately for:

1. number of days of binge alcohol use (H2.1),
2. number of days of benzodiazepine use (H2.2),
3. number of days of stimulant use (H2.3),
4. number of days of marijuana use (H2.4),
5. number of days of other drug use (H2.5).

The analyses without exploring time effects will be executed in the same way described for the analyses of days of risky opioid use in Section 7.2.2. Time trend analyses will be executed as described above in Section 7.6. If the number of days of use is very few, only descriptive analyses will be reported. No multiple imputation will be performed for secondary outcome analyses.

Similar to the days of risky opioid use, descriptive summary statistics of mean, standard deviation, median and range are reported for each of the secondary outcomes of non-opioid substance use above in the past 30 days measured at baseline and monthly for 12 months, in the past 90 days measured at 3, 6, 9, and 12 months, and in the past 180 days measured at 6 and 12 months. Note that there will not be descriptive summary statistics reported monthly for 12 months for other drug use (HLM.HMDRGSP) in the past 30 days since these data are only collected every 3 months. Thus, these will be reported for the past 30 days at 3 months, 6 months, 9 months and 12 months.

Urine Drug Screens at baseline and at 6 and 12 months will be reported by treatment arm in terms of the number of opioid positive UDS results, number of opioid + MOUD positive UDS results, and number of any substance positive UDS results. The number of positive results by individual substance will also be presented. A UDS is considered opioid positive if positive for any of the following substances: opiates (300 ng), oxycodone (100 ng), and fentanyl (20 ng). A UDS is considered opioid + MOUD positive if positive for any of the following substances: opiates (300 ng), oxycodone (100 ng), methadone (300 ng), buprenorphine (10 ng), and fentanyl (20 ng). Urine drug screens will not be used for the primary outcome analysis.

This table will be repeated by visit and prescription for opioids in the past 6 months (yes/no) as reported on the COMM. The table will present the number and percentage of participants at that visit that reported having an opioid prescription in the past 6 months. If a patient participant does not complete the COMM assessment at that visit, the previous COMM response will be used to determine if the patient participant has an opioid prescription. For example, if the patient participant does not do the 12-month COMM assessment but has a 12-month UDS, the COMM response from the 6-month visit will be used to categorize the participant at the 12-month visit. If

the patient participant does not have any COMM responses from the baseline, 6 or 12-month visits but has UDS collected for those visits, it will be assumed the patient participant does not have an opioid prescription for any of the visits.

The following analysis will be done by the LN:

The proportions of individuals whose average number of days (within 30 days) of illicit or nonmedical opioid use during 180 days of follow-up increased relative to their baseline measure (days of use in the 30 days before the baseline assessment, H2.6) will be compared between groups at 6 months and 12 months using chi-square test respectively.

Descriptive summary statistics for COMM score assessed at screening and at 6 and 12 months (H2.7 h), Comparisons of the secondary outcomes between the two treatment arms will be conducted using t-tests or Mann-Whitney tests for continuous measures, chi-square tests for categorical measures.

Generalized estimating equations (GEE) to account for correlation of responses within PCP cluster will be fit for the incidence of moderate to severe OUD (defined as a score of at least 4 on the CIDI, H2.8) and drug use disorder (PDSQ drug items, H2.9) and alcohol use disorder (PDSQ alcohol items, H2.9) assessed at 6 and 12 months separately. Treatment effect is estimated adjusting for baseline level of each measurement. Time trend is evaluated using a time variable.

Self-reported overdose risk behavior will be measured by the overdose risk behavior questionnaire (which gives a numeric score) at baseline, 6, and 12 months. Mean scores will be compared between groups at 6 and 12 months in a random-effect regression model. Also, the total number of non-fatal opioid-related overdose events in the past 3 months will be measured at baseline, 6, and 12 months. Mean numbers of opioid-related overdose events will be compared between groups in a random-effect regression model (H 2.10).

Changes in pain-related symptoms and functioning from baseline as measured by the BPI (which calculates a numeric score) will be compared between treatment arms using Mann-Whitney tests. As the scientific goal is to demonstrate no worsening of pain, a noninferiority test will compare changes in BPI score between treatment and control groups with a minimal clinically important difference of 1 based on the IMMPACT recommendations. A secondary analysis will distinguish the effect of STOP on the change in pain-related symptoms for participants with opioid prescriptions at baseline, and the effect for those who were enrolled solely due to illicit use.

Symptoms of depression, suicidality, anxiety (H2.12), and poor sleep (H2.13) in the past two weeks will be measured at baseline and quarterly (PHQ-8) and at baseline, 6, and 12 months (PROMIS anxiety and sleep measures and PSS). Mean values will be compared between treatment arms in random-effect regression models.

Health-related quality of life (H2.14), and ED and hospital utilization (H2.15) in the past two weeks will be measured at baseline and at 6 and 12 months. Mean values will be compared between treatment arms in random-effect regression models.

Similar models will be fit for the Aim 3 objectives, but these will use provider rather than patient as the unit of observation, so will not need a PCP effect to adjust for within-PCP correlation. Regression models will be used to compare number of prescriptions of high-dose opioids within 12 months of follow-up between treatment arms as well as number of days prescribed during 12 months follow-up. Similar analyses will be done for number of prescriptions for any opioids or benzodiazepines, numbers of naloxone kits prescribed, numbers of urine toxicology tests ordered and completed, and number of patient participants receiving a new diagnosis of OUD.

